### 2.1 Hypothesis and Specific Aims

We hypothesize that the addition of the AQI to AAP will (A) reduce asthma exacerbations, and (B) improve symptom control & quality of life in children with asthma. To test these hypotheses, in this study we will pursue the following specific aims:

- Aim 1: To recruit a pilot cohort of 40 children with asthma. For proof of concept, we will recruit 40 children with asthma from Children's Hospital of Pittsburgh, the only children's hospital serving southwest Pennsylvania (metropolitan area >2.6 million people). Baseline knowledge about the AQI including familiarity, usage, and prior healthcare provider discussion will be assessed.

- Aim 2: To evaluate if the addition of the AQI to AAP reduces asthma exacerbations in a pilot study of children. Participating children (Aim 1) will be randomized to one of two groups. All participants/caregivers will receive an AAP and verbal AQI education. The intervention group will additionally demonstrate the ability to check the AQI, and AQI recommendations will be incorporated onto their written AAP. Children will be followed monthly for 6 months to evaluate adherence to AQI recommendations and assess the frequency of asthma exacerbations, defined per ATS guidelines. Other known factors contributing to asthma exacerbations, such as asthma severity, viral illnesses, allergic triggers will also be monitored.
- Aim 3: To examine whether the addition of the AQI to AAP improves asthma symptom control and quality of life in a pilot study of children. Asthma symptom control will be measured in participating children monthly, and quality of life will be assessed before randomization and at 6 months. Symptom control and quality of life will be evaluated within (before/after intervention) and between groups.

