**Plan activities when and where pollution is lower:**

- Ozone is usually higher on hot summer days in the afternoon & early evening. On days ozone is high, plan your outdoor activities in the morning.
- Particulate pollution can be higher in certain places. Try to avoid exercising where particles are higher. Examples: near busy roadways, during rush-hour traffic, near industrial areas, and when there is smoke in the air.

*Don't let asthma keep you from being active. The CDC recommends 60 minutes of physical activity a day. If asthma is limiting your activity, talk to your doctor!*

Table 1: Study Procedures

VISIT	LOCATION	QUESTIONNAIRE	EMR	MEASURES	SPECIMENS
1	In-person, PCTRC	Intake, AQI intake, PA, ACT or CACT, PAQLQ, tobacco intake	Confirm asthma controller medications, IgE, allergen testing, eosinophils, BAL or sputum eosinophils	Spirometry, FeNO, height, weight	Nasal epithelial cells, urine
2	Telephone	sRQ, AQI_f/u, PA, ACT or CACT.	-	-	-
3	Telephone	sRQ, AQI_f/u, PA, ACT or CACT.,	-	-	-
4	Telephone	sRQ, AQI_f/u, PA, ACT or CACT.	-	-	-
5	Telephone	sRQ, AQI_f/u, PA, ACT or CACT.	-	-	-
6	Telephone	sRQ, AQI_f/u, PA, ACT or CACT.	-	-	-
7	In-person, PCTRC	sRQ, AQI_f/u, PA, ACT or CACT.	-	Spirometry, FeNO, height, weight	Nasal epithelial cells, urine

Intake questionnaire (completed by parent); AQI intake- includes parent portion (completed by parent) + AQI follow up (completed by participant); PA=physical activity (parent and/or participant), ACT=asthma control test ages 12 and older (completed by participant); CACT=childhood asthma control test for ages 8-11 (completed by parent and participant); PAQLQ(s)-pediatric asthma quality of life questionnaire (completed by participant); participant tobacco intake form (completed by participant); sRQ= shortened respiratory questionnaire (completed by parent); AQI\_f/u=AQI follow up questionnaire (completed by participant).

**8.1a Questionnaires:** the risks from questionnaire administration involves social-psychological risk resulting from inadvertent disclosure of medical information and/or questions may create discomfort. Participants and parents do not have to answer any question that they do not wish to answer.

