## 11. CLINICAL MANAGEMENT AND DATA COLLECTION:

Table 2: Summary of Study Protocol

VISIT	LOCATION	TIMING	QUESTIONNAIRE	MEASURES	SPECIMENS
V1	In-person, PCTRC	Start	AQI intake*, Intake, PA, ACT or CACT, PAQLQ, tobacco intake	Spirometry, FeNO, ht, wt	NEC, urine
V2	Telephone	W4, 4 wks post V3 (+/- 7d)	sRQ, AQI_f/u, PA, ACT or CACT.	-	-
V3	Telephone	W8, 4 wks post V3 (+/- 7d)	sRQ, AQI_f/u, PA, ACT or CACT.,	-	-
V4	Telephone	W12, 4 wks post V3 (+/- 7d)	sRQ, AQI_f/u, PA, ACT or CACT.	-	-
V5	Telephone	W16, 4 wks post V3 (+/- 7d)	sRQ, AQI_f/u, PA, ACT or CACT.	-	-
V6	Telephone	W20, 4 wks post V3 (+/- 7d)	sRQ, AQI_f/u, PA, ACT or CACT.	-	-
7V	In-person, PCTRC	W24, 4 wks post V3 (+/- 7d)	sRQ, AQI_f/u, PA, ACT or CACT.	Spirometry, FeNO, ht, wt	NEC, urine

Intake questionnaire (completed by parent); AQI intake- includes parent portion (completed by parent) + AQI follow up (completed by participant); PA=physical activity (parent and/or participant), ACT=asthma control test ages 12 and older (completed by participant); CACT=childhood asthma control test for ages 8-11 (completed by parent and participant); PAQLQ(s)-pediatric asthma quality of life questionnaire (completed by participant); participant tobacco intake form (completed by participant); sRQ= shortened respiratory questionnaire (completed by parent); AQI\_f/u=AQI follow up questionnaire (completed by participant).

Ht=height, wt=weight, NEC=nasal epithelial cells

\*AQI intake form should be completed prior to AQI education/intervention.

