## **11.4 Exit visit (Visit 7)**

Visit 7 will be conducted in person. Eligibility for lung function tests and/or NEC will be assessed prior to study procedures. Questionnaires will be administered, height and weight will be obtained, lung function tests will be obtained (if eligible), and specimens will be collected (if applicable).

If a participant's spirometry demonstrates an FEV1 <80%, the family and participant's managing asthma healthcare provider will be notified. Per family permission, spirometry will be shared with managing asthma healthcare provider. If a participant's FeNO is above 20ppb, with family permission, FeNO will be shared with managing asthma healthcare provider.

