## STATISTICAL PLAN:

Statistical Analysis: Data will be analyzed using SAS (SAS 9.4, Cary, N.C.). Baseline statistics per treatment group will be obtained. Bivariate analysis of covariates (age, sex, race/ethnicity, asthma severity, phenotype (i.e. atopic), socioeconomic status (SES), exposure to primary or secondary tobacco smoke, FeNO, use of controller medication, etc) between groups will be conducted using student t-test or Wilcoxon rank sum and Fisher's exact or Chi-square (where appropriate and based on distribution). Variables with significant differences between groups ( $P<0.05$ ) will be considered for inclusion in multivariate model selection. The effects of physical activity on the outcomes will be compared between groups. Baseline knowledge and usage of AQI will be assessed. Adherence to AQI will also be assessed and compared between groups, with potential stratification by AQI usage. Additionally, differences in weight and BMI will be assessed to evaluate if adherence to AQI promotes sedentarism and leads to increased weight gain. We will evaluate our outcomes (Aims 2 and 3) in three ways. First, we will evaluate the average difference (overall mean) between groups for our primary outcomes using T test or chi-square (where appropriate). Additionally, we will test the average mean difference between each treatment group by multivariate regression (linear for PAQLQ and ACT or CACT, and/or Poisson or logistic regression for mean asthma exacerbations depending on distribution) to allow for covariate adjustment. Second, we will use paired t-tests (or matched Wilcoxon signed-rank) to evaluate the within group effects (6 month mean – baseline) for each primary outcome. Third, to assess the effects over time in our intervention study (correlated repeat measures data), we anticipate analyzing our primary outcomes by generalized linear mixed models (GLMM). For these models, we will first evaluate the distribution of our primary outcome and determine the most appropriate link (e.g. for severe asthma exacerbations: logistic link if there are overall a high proportion of participants with none, or Poisson link if more consistent with count data). A stepwise approach will be used to build all multivariable models. All final models will include age, sex, race/ethnicity, SES, and tobacco smoke exposure. Additionally, the above outcomes will be stratified by age group (8-12y, 13-17y) to determine if the effects are greater in older children for whom the AQI recommendations may be better self-incorporated into outdoor physical activities, vs the younger group who will likely be more reliant on parental checking and activity modification.

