
Power calculations: Power calculations were conducted using G\*Power 354 and SAS (SAS 9.4, Cary, N.C.) using proc glmpower. For mean difference between treatment groups (routine vs. intervention) with sample size of 20 participants per group, two-tailed test, alpha 0.05, we will have  $\geq 90\%$  power to detect a mean difference of 1.05 between groups for mean asthma exacerbations, ACT and C-CACT, and PAQLQ. Our study will provide  $\geq 80\%$  power to detect a mean difference of 0.91. As the clinical difference for ACT is 2-3 points, we anticipate adequate power to detect a clinical difference. The estimated clinically meaningful difference in PAQLQ is 0.5, and our study may be underpowered to detect this small of difference with this analysis. For comparison within each treatment group, comparing the matched difference (end of study- baseline), using the same assumptions above, we will have  $\geq 90\%$  power to detect a mean difference of 0.76, and  $\geq 80\%$  power to detect a mean difference of 0.66. Therefore, we expect better ability to detect changes in PAQLQ within the groups than between them. For repeat measures, we estimated our power using proc glmpower using F test based on Hotelling-Lawley trace. We estimated a study allocation of 1:1, alpha 0.05, repeated measures at 1, 2, 3, 4, 5 months, lear correlation structure with base correlation 0.85 & decay rate of 1, with an estimated mean difference of 2, standard deviation of 2, which provides a  $\geq 90\%$  power for a treatment group size of 12 for overall mean and n=26 for time\*treatment.

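### Aim 3 calls for a 6-month PAQLQ, but neither visit table schedules one at Visit 7 or at any other follow-up visit

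*Combined protocol and SAP*

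**What the plan says.** **Where a 6-month PAQLQ is needed.**

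- Section 2.1, Aim 3: "quality of life will be assessed before randomization and at 6 months". The aim then calls for comparisons both within and between groups.
- Section 2.2 gives PAQLQ(S) as the quality-of-life measure and names no other. Section 2.3 says an interviewer administers it.
- Statistical Plan, between-group regression: "linear for PAQLQ and ACT or CACT". The same section plans paired tests of 6 months against baseline for each primary outcome.
- Power calculations: between-group detectable differences are given first and cover PAQLQ. The within-group figures follow, "comparing the matched difference (end of study- baseline"), and the section concludes that PAQLQ change is better detected within groups than between them.

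**What the schedules list.**

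- Table 1, Visit 1: "Intake, AQI intake, PA, ACT or CACT, PAQLQ, tobacco intake". Table 2, Visit 1: "AQI intake*, Intake, PA, ACT or CACT, PAQLQ, tobacco intake". Both include PAQLQ.
- Tables 1 and 2, Visit 7: "sRQ, AQI_f/u, PA, ACT or CACT". PAQLQ is absent. In Table 2 this is the row timed "W24, 4 wks post V3 (+/- 7d").
- Section 11.4, exit visit: "Questionnaires will be administered, height and weight will be obtained", with no instrument named.

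**The concern.** The aims and the visit schedules disagree on whether a named outcome is measured after baseline. A coordinator who needs to know which questionnaires to give at Visit 7 has only the two tables to consult, and both leave PAQLQ out.

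If the tables are followed, PAQLQ exists only at Visit 1, before the intervention can have had any effect. No change score can be formed. A between-group comparison of the available values would compare the groups at baseline and say nothing about the intervention. The quality-of-life part of hypothesis B and Aim 3 would go unanswered. Visit 7 closes follow-up, so an omission noticed afterwards could be made good only outside the week-24 window of plus or minus 7 days.

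**Working it through.** **1. Aim, tables and text side by side**

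| Item | Visit 1 | Visits 2–6 | Visit 7 |
|---|---|---|---|
| Quality of life, per Aim 3 | yes | not required | yes |
| PAQLQ, Table 1 | yes | no | **no** |
| PAQLQ, Table 2 | yes | no | **no** |
| ACT or C-ACT, both tables | yes | yes | yes |
| Spirometry, FeNO, height, weight, both tables | yes | no | yes |
| Nasal cells, urine, both tables | yes | no | yes |

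PAQLQ is in 1 of 7 rows of each table and in 0 of the 6 follow-up rows. The other Visit 1 measures that the plan wants repeated at exit do reappear in the Visit 7 row. The gap is confined to the questionnaire cell, which repeats the telephone-visit list.

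**2. Could it be a text-extraction fault?** Unlikely. Both tables are legible and agree with each other, and their Visit 7 measures and specimens cells are filled as expected. The same single item is missing from both.

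**3. Does other text supply it?** Section 11.4 refers to questionnaires in general. Section 11.2 uses the same general wording for Visit 1, so in both places the choice of instruments is left to the tables. No other available text schedules PAQLQ at exit. Figures 3 and 4 are not shown. If either lists it, that figure would disagree with both tables.

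**4. The plan's own power figures**

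Inputs from the power calculations: 20 per group, two-sided alpha 0.05. No SD is given for these figures, so SD = 1 is assumed and all differences are in SD units. Power comes from the noncentral t distribution:

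- within group: n − 1 degrees of freedom, noncentrality d·√n
- between groups: 2n − 2 degrees of freedom, noncentrality d·√(n/2)

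| Comparison | d | Power in the plan | Power recomputed |
|---|---|---|---|
| Within, n = 20 | 0.66 | 80% | 79.9% |
| Within, n = 20 | 0.76 | 90% | 89.7% |
| Between, 20 per group | 0.91 | 80% | 80.1% |
| Between, 20 per group | 1.05 | 90% | 89.9% |

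The figures reproduce to rounding. They presuppose a follow-up PAQLQ from all 20 children in each group.

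**5. What the tables deliver**

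Followed as written, they give 0 of 20 per group, or 0 of 40 in all. With n = 0 no 6-month mean, change or group effect can be estimated.

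**6. Partial collection (assumption, for illustration only)**

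If PAQLQ were obtained from some children only, the difference detectable at 80% power, in SD units, would be:

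| Follow-up PAQLQ per group | Within group | Between groups | Within-group power at d = 0.66 |
|---|---|---|---|
| 20 | 0.660 | 0.909 | 80% |
| 15 | 0.778 | 1.060 | 66% |
| 10 | 0.996 | 1.325 | 46% |

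The counts of 15 and 10 are not in the documents. The plan's clinically meaningful PAQLQ difference of 0.5 cannot be set directly beside these values, because it is not stated in SD units and no PAQLQ SD is given.

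**The case against.** The strongest reply is that the intent is plain and the tables are imperfect summaries. Aim 3 states the 6-month time point outright, nothing says that PAQLQ is not collected at exit, and section 11.4 is compatible with collecting it. Table 2 has other drafting slips: every follow-up row is timed from Visit 3, including Visits 2 and 3 themselves. This is one site with 40 children, and study-visit data are overseen closely. The data-capture form may already carry PAQLQ at Visit 7, and section 13.2 provides an alert for unanswered required questions. Nothing in the documents suggests that staff would split between two readings, and the partial-collection figures would apply to missing data from any cause.

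Much of this is fair. A drafting omission is the likeliest explanation, and loss of the data is a risk, not a certainty. The partial-collection figures only illustrate the cost. It is also true that only Aim 3 names the 6-month time point for quality of life; the statistical plan needs it by implication, through the paired test, the PAQLQ regression and the statement about PAQLQ change.

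None of it removes the contradiction. The tables are the only place that lists instruments by visit, and two of two omit this one. The alert covers questions left blank on a form; the documents do not show that it would reveal an instrument never assigned to the visit. An interviewer-administered questionnaire also has to be planned for.

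**Conclusion.** The concern holds. Aim 3 and both visit tables cannot all be right, and the statistical plan depends on the measurement that the tables leave out. If the tables are followed, 0 of 40 children have an on-schedule 6-month PAQLQ, and the quality-of-life part of Aim 3 cannot be analysed within or between groups. That conclusion rests on the text alone and needs no distributional assumption. Whether the data would in fact be lost depends on the Visit 7 form and on Figures 3 and 4, which cannot be seen. The tables need correcting in either case. Because a named outcome is at stake and Visit 7 is the last opportunity to measure it on schedule, the correction is essential.

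**What to change.** - Add PAQLQ to the Visit 7 questionnaire cell of Table 1 and of Table 2.
- Name PAQLQ in section 11.4 among the questionnaires given at the exit visit.
- Confirm that the Visit 7 data-capture form includes PAQLQ as a required instrument, and check that Figures 3 and 4 agree.

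The cost is one entry in each of two tables, one phrase of text, a check of one form and a look at two figures. For participants it is a few minutes of interview at an in-person visit already scheduled. Sample size, analyses and power figures stay as they are.

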## 2.2 Outcome Measures

- **Asthma exacerbations** will be defined by ATS guidelines as:
  - (1) Severe:
    - a) requiring 3 or more days of systemic corticosteroids  
**or**
    - b) ED visit/hospitalization for asthma treated with systemic steroids (any duration)
  - (2) Moderate:
    - a) asthma symptoms + increased rescue medication both for at least 2 days  
**or**
    - b) a visit to ED/urgent care/doctor office or clinic for which sick care was sought for asthma but no systemic steroids were given

[figure not shown]
(note: Inclusion of urgent care/doctor office or clinic for acute asthma care is interpretation of PI and not explicitly stated in ATS guidelines, this does not include routine visits)
- **Asthma control** will be defined used validated asthma control tests: ACT for children 12 years and older and CACT for children 8-11 years.
- **Asthma quality of life** will be assessed via the validated pediatric asthma quality of life questionnaire (PAQLQ(S)).

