## **11.3 Trial Phase (Visits 2-6)**

The participants will be followed monthly (every 4 weeks, +/- 7 days) with interval follow up telephone calls. Questionnaires will be administered during the telephone calls. Throughout the trial, participants will be reminded that participation in the research study does not replace clinical care. Moderate and severe asthma exacerbations will be asked about on monthly questionnaires. If a participant reports 3 severe asthma exacerbations (so defined by ATS criteria as an event requiring 3 or more days of systemic steroid treatment for asthma or an ED visit/hospitalization during which a steroid was prescribed), the participant's managing asthma healthcare provider will be notified. Additionally, if a participant has more 3 consecutive ACT or CACT scores that are equal to or less than 19, which is the threshold concerning for asthma control, the participant's managing healthcare provider will be notified.

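### An office, clinic or urgent-care asthma visit treated with 1-2 days of systemic steroids can count as no exacerbation, although the same visit without steroids is moderate

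*Combined protocol and SAP*

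**What the plan says.** Section 2.2 of the protocol gives two routes to each class of exacerbation.

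- **Severe (a):** "requiring 3 or more days of systemic corticosteroids", in any setting.
- **Severe (b):** an ED visit or hospitalization for asthma treated with systemic steroids, for any length of time.
- **Moderate (a):** "asthma symptoms + increased rescue medication both for at least 2 days". No visit is needed, and nothing is said about steroids.
- **Moderate (b):** "a visit to ED/urgent care/doctor office or clinic for which sick care was sought for asthma but no systemic steroids were given".

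A note under the definition adds: "Inclusion of urgent care/doctor office or clinic for acute asthma care is interpretation of PI and not explicitly stated in ATS guidelines". It also excludes routine visits.

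Section 11.3 restates severe as "an event requiring 3 or more days of systemic steroid treatment for asthma or an ED visit/hospitalization during which a steroid was prescribed". Urgent care, office and clinic are again absent.

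Aim 2 (Section 2.1) is to "assess the frequency of asthma exacerbations, defined per ATS guidelines", and names no class. The Statistical Plan proposes "Poisson or logistic regression for mean asthma exacerbations depending on distribution", also without a class. Its one class-specific example of a model is for severe exacerbations.

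**The concern.** The investigator's added settings (urgent care, office, clinic) were put into moderate (b) but not into severe (b), and moderate (b) admits only visits without steroids. A steroid-treated visit in one of these settings therefore has no visit-based route unless the course reaches 3 days. A visit that led to a short steroid course can then score lower than one that led to none. Nothing in the documents presents this as intended.

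Exacerbation reduction is hypothesis (A) and the outcome of Aim 2. Any analysis of moderate, total or any exacerbation depends on this rule. The trial is non-blinded, the research coordinator knows the assignment (Section 11.2), and exacerbations are captured on a parent-completed questionnaire. An event type without a clear class invites case-by-case decisions by people who know the arm. No direction of bias is claimed.

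**Working it through.** The plan states no figure on this point, so there is nothing to reproduce. The check applies the four criteria of Section 2.2 to every combination of three factors:

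- setting: ED, or urgent care/office/clinic (the settings named in moderate (b));
- days of systemic steroids: 0, 1-2, or 3 or more;
- moderate (a): met or not met.

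This gives 2 × 3 × 2 = 12 cells. Where a cell meets both definitions, both are shown.

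| Setting | Steroid days | (a) not met | (a) met |
|---|---|---|---|
| ED | 0 | moderate | moderate |
| ED | 1-2 | severe | severe and moderate |
| ED | 3 or more | severe | severe and moderate |
| Urgent care/office/clinic | 0 | moderate | moderate |
| Urgent care/office/clinic | 1-2 | **none** | moderate |
| Urgent care/office/clinic | 3 or more | severe | severe and moderate |

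The bold cell fails each route in turn:

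- severe (a), because the course is under 3 days;
- severe (b), because the setting is neither ED nor hospital;
- moderate (b), because steroids were given;
- moderate (a), by construction.

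Counts under the current rule and three alternatives:

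| Rule | Severe only | Moderate only | Both | None |
|---|---|---|---|---|
| As written | 3 | 5 | 3 | 1 |
| Remove the no-steroid condition from (b), nothing else | 0 | 6 | 6 | 0 |
| Remove it, and define moderate as not severe | 6 | 6 | 0 | 0 |
| Extend severe (b) to urgent care/office/clinic, highest class counts | 8 | 4 | 0 | 0 |

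The third rule leaves severe membership unchanged: 3 + 3 = 6 cells before and 6 after. The fourth raises it to 8.

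Cells are not event rates. The only size that can be stated is per event. With 20 children per group (Power calculations), one uncounted event lowers that arm's mean by 1/20 = 0.05 exacerbations per child. If it was the child's only event, the arm's proportion with any exacerbation falls by 1/20 = 5 percentage points.

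**The case against.** The strongest reply is that the gap is narrow. Three things must coincide: a non-ED setting, a course of 1-2 days, and symptoms and increased rescue use that do not both last 2 days. Moderate (a) will capture some of these visits, the rule is the same in both arms, and this is a 40-child pilot. The 0.05 figure also holds for any single event of any kind. If the detectable difference of 0.91 in the Power calculations is read as events per child (an assumption, since the figures also fit standard-deviation units), a shift of that size would need 0.91 × 20 = 18.2, or about 18, events lost from one arm. All of this stands as a limit on likely impact. It does not show that the rule works, because the documents do not say how many visits moderate (a) would capture.

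A second reply is that the note only explains why the settings are listed, so steroid-treated visits there may be meant to count by duration or through (a) alone. That reading is possible, but the protocol does not state it. It would still leave a steroid-treated visit uncounted where an untreated one counts.

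A third reply is that the remedy is incomplete. This is partly right. Two cases outside the 12 cells stay unclassified when (a) is not met: a 1-2 day course with no visit, and a hospitalization without steroids that involved none of the visits listed in moderate (b).

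**Conclusion.** The concern holds. As written, Section 2.2 gives no visit-based class to an urgent-care, office or clinic asthma sick visit treated with 1-2 days of systemic steroids, and no other section supplies one. This follows from the wording alone and needs no assumption about rates. It affects analyses of moderate, total or any exacerbation, but not severe-only analyses. The number of affected events, and hence any effect on power or on the rate ratio, cannot be derived from the documents. The change should be made because the defect sits in the definition of the Aim 2 outcome and costs almost nothing to correct, not because a large effect has been shown.

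**What to change.** Make two changes in Section 2.2, for outcome coding only, before any events are classified:

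1. Define a moderate exacerbation as an event that does not meet the severe definition and meets (a) or (b).
2. Remove from (b) the condition that no systemic steroids were given.

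Both are needed. The second alone closes the gap but doubles the cells meeting both classes from 3 to 6. Together they give every ED, urgent-care, office or clinic sick visit for asthma exactly one class. The severe definition and the Section 11.3 notification trigger stay as they are.

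The sponsor may prefer another class for these visits, provided one is stated. Extending severe (b) would also close the gap, but it would change the severe count and break the match with the severe wording in Section 11.3. The protocol should also say whether a 1-2 day steroid course with no visit, and a hospitalization without steroids, are meant to count only through (a).

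The cost is one sentence in Section 2.2 and a matching coding rule for the shortened respiratory questionnaire. The moderate class may move a little further from the cited guideline, which cannot be checked from these documents. The existing note already acknowledges a departure for the added settings and could be extended to cover this one.
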